Title	Effect of immuno-nutrition on systemic inflammation in people receiving haemodialysis: a pilot study.
Acronym	
Short title	Immuno-nutrition in haemodialysis
Chief Investigator	[name]
Objectives	
 1. To investigate whether provision of an immuno-nutrition supplement decreases systemic inflammatory status in people on haemodialysis. 2. To investigate the effect of an immuno-nutrition supplement on biochemical blood variables, body composition, dietary intake and muscle strength in people on haemodialysis.
Study Configuration	Single-centre, non-randomised, interventional pilot study.
Setting	Secondary care
Sample size estimate	As a pilot study power calculations are not appropriate
Number of participants	15
Eligibility criteria	
Inclusion criteria:
 
 • CRP level >5 mg/L. • Age: ≥ 18 years (no upper age limit). • At least three haemodialysis sessions per week for ≥ 3 hours using a biocompatible dialyser. • Able to give informed consent. 
Exclusion criteria:
 
 • Treatment with drugs that cause immunosuppression. • Non-English speakers or those with special communication needs. • Pregnancy, breast feeding or intending pregnancy. • Expected survival <6 months. • Hospitalisation at the time of screening. • Known intolerance or allergy to oral nutritional supplement (or isolated ingredients). • Pre-dialysis serum potassium >5.0 mmol/L. • Unable to provide informed consent.

Description of interventions	Dietitian supervised nutritional support with an immuno-nutrition supplement (Oral Impact®, Nestle)
Duration of study	Duration of individual study participation: 6 weeks. Overall study duration: 3 months.
Methods of analysis	To compare baseline versus final evaluations, a Wilcoxon test or paired t-test will be used in the case of dimensional variables, and McNemar test in the case of categorical variables. Inter-group comparisons will be performed using a Mann-Whitney test or Student t-test for continuous variables and χ^2 test or Fisher's exact test for categorical variables. A p value <0.05 will be considered to have statistical significance.

ABBREVIATIONS

AE	Adverse Event
BMI	Body Mass Index
CI	Chief Investigator
CRF	Case Report Form
CRP	C Reactive Protein
GCP	Good Clinical Practice
HGS	Handgrip strength
NHS	National Health Service
ONS	Oral Nutritional Supplement
PIS	Participant Information Sheet
REC	Research Ethics Committee

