Immuno-nutrition supplements are high in energy and protein (similar to conventional ONS), but also contain a unique combination of nutrients (i.e., omega-3 fatty acids, L-arginine and nucleotides), each acting in a complementary way to suppress inflammation, while concomitantly enhancing immune function [21]. Immuno-nutrition supplements (specifically Oral Impact®, Nestle) have been mostly used in pre-surgical settings, and previous studies conducted in cancer populations have reported a decrease in post-operative infections and length of hospitalisation, underpinned by evidence of a decrease in systemic inflammation [22].

This will be the first study to explore the potential effect of an immuno-nutrition supplement (Oral Impact®, Nestle) to address systemic inflammation in people receiving haemodialysis. The findings of this pilot study will help to design a randomised controlled clinical trial investigating whether a treatment bundle of resistance exercise training and immuno-nutrition supplementation can improve skeletal muscle mass, other markers of nutritional status and quality of life in people on haemodialysis.

STUDY OBJECTIVES AND PURPOSE

PURPOSE

The purpose of the present study is to investigate the impact of an immuno-nutrition supplement on systemic inflammation in people receiving haemodialysis.

PRIMARY OBJECTIVE

To investigate whether provision of an immuno-nutrition supplement decreases systemic inflammatory status in people on haemodialysis.

SECONDARY OBJECTIVES

To investigate the effect of an immuno-nutrition supplement on biochemical blood variables, body composition, dietary intake, skin autofluorescence (SAF) and muscle strength in people on haemodialysis.

DETAILS OF PRODUCT(S)

Description

Oral Impact® is a powdered oral nutritional supplement that contains a unique combination of ingredients with immuno-modulating properties, namely omega-3 fatty acids, arginine and nucleotides, as well as soluble fibre.

Manufacture

Oral Impact® is manufactured by Nestlé Health Science, Reg. Trademark of Société des Produits Nestlé S.A. OIDC 001

Packaging and labelling

Oral Impact® comes in a box that contains 5 sachets x 74g. Please see Appendix 1 for images of packaging and labelling.

Storage, dispensing and return

Oral Impact® will be stored unopened in a locked room which should be cool, dry and away from light and humidity. Access to the room will be restricted to members of the research team.

Known Side Effects

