Participants may be withdrawn from the study either at their own request or at the discretion of the Investigator. The participants will be made aware that this will not affect their future care. Participants will be made aware (via the PIS and consent form) that should they withdraw the data collected to date cannot be erased and may still be used in the final analysis.

Participants will not be replaced if they withdraw from the study.

Informed consent

The process for obtaining participant informed consent will be in accordance with the Research Ethics Committee (REC) guidance, Good Clinical Practice (GCP) and any other regulatory requirements that might be introduced. The investigator or their nominee and the participant shall both sign and date the consent form before the person can participate in the study.

The participant will receive a copy of the signed and dated consent form and the original will be retained in the Study records. A second copy will be filed in the participant's medical notes and a signed and dated note made in the notes that informed consent was obtained for the study. The decision regarding participation in the study is entirely voluntary. The investigator or their nominee shall emphasize to them that consent regarding study participation may be withdrawn at any time without penalty or affecting the quality or quantity of their future medical care, or loss of benefits to which the participant is otherwise entitled. No study-specific procedures will be done before informed consent has been obtained.

The investigator will inform the participant of any relevant information that becomes available during the course of the study and will discuss with them whether they wish to continue with the study. If applicable they will be asked to sign revised consent forms.

If the consent form is amended during the study, the investigator shall follow all applicable regulatory requirements pertaining to approval of the amended consent form by the REC and use of the amended form (including for ongoing participants).

STUDY REGIMEN

Once participants have given their informed consent, they will be advised to take **daily** one sachet (74 g) of the immuno-nutrition supplement (Oral Impact®, Nestle) dissolved in 125 ml of water and will be followed-up for 6 weeks.

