Participants will receive individualised (to patient needs and food preferences) dietetic advice formulated and delivered by an experienced renal dietitian under an honorary NHS research contract ([name]), who is a member of the research team and will be supervised by an NHS renal dietitian, aiming to achieve estimated nutritional requirements for people on haemodialysis (i.e., energy: 30-35 kcal/kg/day, and protein intake: 1.0-1.2 g/kg/day) [23]. Each dietetic advice provided to participants will also be reviewed by the NHS clinical renal dietitians who are members of the participants' usual clinical care team.

Consumption of the immuno-nutrition supplement will be supervised during haemodialysis sessions (thrice weekly) and self-reported (written and counting empty sachets) on non-dialysis days. Participants will receive precise oral instructions on how and when to take the supplement with close monitoring by the renal dietitian on the research team to encourage adherence to the intervention.

Three-day food diaries (i.e., one dialysis day, one non-dialysis day and one weekend day) will be completed by the participants at baseline, 3 and 6 weeks of follow-up, and will be analysed (Microdiet, Downlee Systems Ltd, UK) to assess compliance with the advice provided and to assess energy, protein and fat intake across the study period.

Data collection procedures

Hospital electronic medical records will be used to collect relevant baseline participant characteristics, including age, sex, ethnicity, time since dialysis initiation, dialysis adequacy,

current medication, presence of diabetes and history of cardiovascular disease. Information regarding educational level, occupation status, and history of smoking will be obtained by direct interview with the participants at the time of the baseline assessment. A blood sample will be taken weekly pre-dialysis after commencing the immuno-nutrition supplement to monitor serum potassium. Results from routine clinical blood tests will be recorded at baseline and 6 weeks of follow-up and will include haemoglobin, urea, creatinine, potassium, phosphate, calcium, sodium, albumin, total proteins, total cholesterol, triglycerides and CRP.

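### The purpose and objectives credit the supplement with changes that belong to supplement plus dietetic advice, and the dietary-intake endpoint does not say whether the sachet is counted

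*Combined protocol and SAP*

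**What the plan says.** **What is to be learned.** The Purpose section reads: "The purpose of the present study is to investigate the impact of an immuno-nutrition supplement on systemic inflammation". The Primary objective asks whether giving the supplement lowers inflammatory status. The Secondary objectives ask for its effect on biochemistry, body composition, dietary intake, skin autofluorescence and muscle strength. None of them mentions dietetic advice. The primary outcome and the stem of the secondary endpoints are worded as change after six weeks on the supplement.

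**What participants receive.** Study Regimen gives each participant a daily dose of "one sachet (74 g) of the immuno-nutrition supplement". It then adds: "Participants will receive individualised (to patient needs and food preferences) dietetic advice formulated and delivered by an experienced renal dietitian". That dietitian belongs to the research team, and the advice aims at "energy: 30-35 kcal/kg/day, and protein intake: 1.0-1.2 g/kg/day". On its relation to routine care, the section says "Each dietetic advice provided to participants will also be reviewed by the NHS clinical renal dietitians who are members of the participants" (the sentence goes on to name their usual care team). The Synopsis, under Description of interventions, has "Dietitian supervised nutritional support with an immuno-nutrition supplement".

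**How it is analysed.** Study Design describes one non-randomised group on one regimen. Statistics compares baseline with final values by paired tests.

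**How intake is measured.** Dietary intake is a secondary endpoint taken from three-day food diaries at baseline, 3 and 6 weeks. The diaries are analysed "to assess compliance with the advice provided and to assess energy, protein and fat intake across the study period". Sachet consumption is tracked separately: supervised at dialysis sessions, and "self-reported (written and counting empty sachets) on non-dialysis days". Nothing says whether the sachet's energy and protein enter the diary totals.

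**The concern.** There are two linked problems.

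(a) *Attribution.* The Purpose and objectives use causal words (impact, effect, decreases) about one component, while everyone receives two components at once. Following that wording leads to a conclusion about the supplement that this design cannot support. The protocol says the findings will inform a randomised trial of immuno-nutrition with resistance exercise, and that description does not mention dietetic advice. A supplement-only conclusion could therefore carry forward into its design.

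(b) *Definition of intake.* The product under study is itself food energy and protein. If the sachet counts, measured intake can rise because the product was taken, even when the person eats exactly as before. If it does not count, intake is understated against the per-kg targets. Whoever runs the diet software would settle this after the data are in.

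**Working it through.** **Part (a): passages side by side.**

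- Named in the Purpose and objectives: the supplement.
- Delivered under Study Regimen: the supplement plus individualised advice with intake targets, to all participants over the same six weeks.
- Available comparison: each participant's baseline against final value. There is no control group and no advice-only period. Statistics also lists inter-group tests, but the documents define no second treatment group.

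The observed mean change is therefore supplement + advice + anything else that changes over six weeks, and no planned analysis separates these terms. The Background reports that advice and conventional supplements *together* improved BMI, albumin, prealbumin and amino acid profiles. That makes an effect of the package on BMI and albumin plausible, but it does not isolate advice and says nothing about CRP or cytokines. No size can be given for the advice on any endpoint.

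**Part (b): arithmetic.**

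Inputs from the documents: 309 kcal and 18 g protein per 74 g sachet (Appendix 1); one sachet daily and the per-kg targets (Study Regimen); n = 15. Assumed: body weight 70 kg, range 60–80 kg.

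1. *Check of the label figures.* Scaling the other column of the table by 0.74 gives 418 × 0.74 = 309.3 kcal and 24 × 0.74 = 17.8 g. From macronutrients: 7.4×9 + 41×4 + 3×2 + 18×4 = 308.6 kcal. The label values reproduce.

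2. *Share of target* = sachet ÷ (target per kg × weight).

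| Weight | Energy target, kcal | Sachet share | Protein target, g | Sachet share |
|---|---|---|---|---|
| 60 kg | 1,800–2,100 | 14.7–17.2% | 60–72 | 25.0–30.0% |
| 70 kg | 2,100–2,450 | 12.6–14.7% | 70–84 | 21.4–25.7% |
| 80 kg | 2,400–2,800 | 11.0–12.9% | 80–96 | 18.8–22.5% |

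3. *Against the width of the target range.* Protein at 70 kg: 18/70 = 0.26 g/kg, against a range 1.2 − 1.0 = 0.2 g/kg wide. The sachet exceeds the whole range below 18/0.2 = 90 kg. Energy: 309/70 = 4.4 kcal/kg, against 35 − 30 = 5 kcal/kg.

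4. *Direction.* Let F be the change in food intake and S the sachet's contribution. Total change is F + S. Whenever −S < F < 0, food-only intake falls while total intake rises. At full adherence S is 309 kcal and 18 g. At 50% consumption, the withdrawal threshold, it is 154.5 kcal and 9 g. For example, a 100 kcal fall in food with full adherence gives −100 kcal on one definition and +209 kcal on the other.

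5. *Significance, illustration only.* Assume no mean change in food, full adherence, a sachet-free baseline diary and a two-sided paired t-test at 0.05 with n = 15. Counting the sachet then gives power of 96%, 79% or 61% to declare an energy rise if the SD of change is 300, 400 or 500 kcal/day. For protein it is 99%, 90% or 74% at 15, 20 or 25 g/day. The SDs are assumptions; the documents give none.

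**The case against.** The strongest reply is that nothing is hidden. The Synopsis and Study Regimen describe the dietitian's role openly, the study is declared a non-randomised pilot, and its main limitation is the missing control group, which no renaming cures. Total intake is also the natural reading of the diary endpoint, and dietary intake is one secondary endpoint group among five. Most of this stands and is why the point is minor. What it does not answer is that the Purpose and objectives still ask a narrower causal question than the regimen can address, and that the counting rule is natural but unwritten.

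Four stronger readings are tempting and are not supported:

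- *That the endpoints themselves attribute change to the supplement.* Their wording is temporal: change after six weeks of treatment. Only the Purpose and objectives are causal, and none says the supplement acts by itself.
- *That the advice is new to participants, or biases CRP and cytokines by a known amount.* Usual-care dietitians review the advice, and the documents do not say how it differs from routine care.
- *That counting the sachet moves participants from non-compliant to compliant.* At 70 kg, food protein of 52 to <70 g (70 − 18 = 52) or energy of 1,791 to <2,100 kcal (2,100 − 309 = 1,791) would cross the lower limit. But that assumes compliance means reaching that limit. Study Regimen sets no such threshold; it assesses compliance with individualised advice that aims at the ranges.
- *That the two diary uses require different totals.* One total can serve both. Food-only intake answers an additional question, whether eating changed.

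**Conclusion.** Both parts hold, at minor severity. Any before-after change in this study belongs to supplement plus dietetic advice and is uncontrolled, so the Purpose and objectives claim more than the design can show. The size of the advice's contribution is unknown, and the sachet figures lend no weight to that part.

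The intake endpoint lacks a counting rule that is worth up to 309 kcal and 18 g protein per day at full adherence. This is about an eighth to a seventh of the energy target and a fifth to a quarter of the protein target at 70 kg, and it can change the sign of the result. These shares rest on assumed body weights and on the Tropical flavour label. The definition of the primary outcome, its analysis and the sample size are unaffected.

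**What to change.** 1. Reword the Purpose, the objectives and the planned conclusions to match the Synopsis and Study Regimen: the intervention evaluated is the supplement plus individualised dietetic advice, reported as an uncontrolled before-after change and not credited to the supplement by itself. Add a brief description of usual dietetic care at the unit, so that readers can judge what the study advice adds.
2. Give all participants the same instruction on whether to write the sachet in the diary, so that it is always identifiable and never counted twice. Record sachet intake for the diary days themselves; the protocol does not say that the existing sachet record is dated.
3. Define food-plus-sachet intake, using the label values of the flavour supplied, as the main intake variable and the one compared with the targets. Report food-only intake as a descriptive companion for change in eating, without a second significance test. Do not describe the sachet's own content as a change in eating.

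Cost: a narrower headline claim, one extra diet-software total per diary (at most 15 × 3 = 45 diaries), and a dated sachet entry on diary days if the present record lacks one.

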No known side effects. However, Oral Impact® is unsuitable for people with cow's milk protein allergy and those who are severely septic. Oral Impact® should not be mixed with medication and food.

STUDY DESIGN

This will be a single-centre, non-randomised, interventional pilot study where people on haemodialysis will receive an immuno-nutrition supplement (Oral Impact®, Nestle) for 6 weeks.

STUDY CONFIGURATION

Primary outcome

Change in C reactive protein (CRP), and pro- and anti-inflammatory cytokine levels (via multiplex plasma analysis) after 6 weeks of treatment with an immuno-nutrition supplement.

Secondary endpoints

Change after 6 weeks of treatment with an immuno-nutrition supplement in:

- Biochemical blood variables including haemoglobin, urea, creatinine, potassium, phosphate, calcium, sodium, albumin, total proteins, total cholesterol and triglycerides.
- Body composition assessed with bioelectrical impedance analysis and BMI.
- Dietary intake assessed with 3-day food diaries.
- Muscle strength assessed with handgrip strength (HGS).
- SAF levels.

Safety endpoints

- AEs that occur will be reported during the study.
- Participant reported tolerability of the immuno-nutrition supplement.
- Monitoring of pre-dialysis serum potassium levels.

STUDY MANAGEMENT

The Chief Investigator (CI) has overall responsibility for the study and shall oversee all study management. The study will be co-ordinated from the University of Nottingham campus at the Royal Derby Hospital. Data will be collected at the Renal Dialysis Unit of the Department of Renal Medicine at the Royal Derby Hospital (University Hospitals of Derby and Burton NHS Foundation Trust) and stored at the University of Nottingham.

The CI and Co-investigators are responsible for study planning, recruitment, consenting, data collection, handling and interpretation. The data custodian will be the CI, [name].

DURATION OF THE STUDY AND PARTICIPANT INVOLVEMENT

Participant recruitment will begin in January 2022 once all necessary approvals are in place, with an anticipated total recruitment and intervention delivery period of 3 months (i.e., end of March 2022). The study will end when the last participant completes their final study visit.

SELECTION AND WITHDRAWAL OF PARTICIPANTS

Recruitment

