Blood samples will be taken at the Renal Dialysis Unit and transferred to the local NHS laboratory (which is serviced and managed according to national UKAS standards and governance frameworks) at the Royal Derby Hospital for routine biochemistry and

haematology testing. These samples will be labelled according to NHS requirements. No DNA or RNA extraction will occur as part of this study.

STATISTICS

Statistical analyses will be performed using SPSS version 28.0. Data will be presented as mean \pm standard deviation, median (interquartile range), or percentages, as appropriate. To compare baseline versus final evaluations, a Wilcoxon test or paired t-test will be used in the case of dimensional variables, and McNemar test in the case of categorical variables. Intergroup comparisons will be performed using Mann-Whitney test or Student t-test for continuous variables and χ^2 test or Fisher's exact test for categorical variables. An alpha error of less than 0.05 will be judged to be significant. All data will be analysed on University of Nottingham computers and backed up regularly.

Sample size and justification

A formal power calculation is not appropriate for this pilot study design, and consequently, the sample size has been selected on a pragmatic basis. We will aim to recruit 15 participants in total.

Procedures for missing, unused and spurious data

All missing data will be explained. If a space on the Case Report Form (CRF) is left blank because the procedure was not done or a question was not asked, "N/D" will be recorded. If the item is not applicable to the individual case, "N/A" will be recorded. All entries will be printed legibly in black ink. If any error is made in data entry, to correct the error, a single straight line will be drawn through the incorrect entry and the correct data entered above it. All such changes will be initialled and dated. Errors will not be erased or altered by any other method. For clarification of illegible or uncertain entries, the clarification will be printed above the item, initialled and dated. Correction fluid will not be used.

Definition of populations analysed

The study will analyse the following populations:

- Safety set: All participants who underwent at least one study session.
- Full Analysis set: All participants, who participated in at least one study session and for whom at least one post-baseline assessment of the primary endpoint is available.

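### Tests between groups are planned in a one-group study, and the primary outcome is CRP plus unlisted, unranked cytokines judged at 0.05 with no multiplicity rule and no confidence interval for the change

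*Combined protocol and SAP*

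**What the plan says.** **Design.** The Study Design section reads: "This will be a single-centre, non-randomised, interventional pilot study where people on haemodialysis will receive an immuno-nutrition supplement". Under Study Regimen, everyone who consents is advised to take the supplement. There is no comparator, and no subgroup is named for analysis.

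**Tests between groups.** The Statistics section plans "Intergroup comparisons will be performed using Mann-Whitney test or Student t-test for continuous variables", with chi-square or Fisher's exact tests for categorical variables. The Synopsis (Methods of analysis) repeats it: "Inter-group comparisons will be performed using a Mann-Whitney test or Student t-test for continuous variables". Neither place says which groups.

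**Primary outcome.** Under Study Configuration it is "Change in C reactive protein (CRP), and pro- and anti-inflammatory cytokine levels (via multiplex plasma analysis) after 6 weeks of treatment". CRP is named. The cytokines are not listed, no marker leads, and no favourable direction is given for the anti-inflammatory ones. Data collection procedures take plasma before and after dialysis at baseline and week 6, without saying which sample counts. The primary objective is directional: "To investigate whether provision of an immuno-nutrition supplement decreases systemic inflammatory status in people on haemodialysis".

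**Decision rule and reporting.** Significance is set at 0.05 in both places, with no sidedness, no multiplicity rule and no statement that testing is exploratory. Paired comparisons use a Wilcoxon or a paired t-test, with no rule for choosing. Summaries are means with SDs, medians with interquartile ranges, or percentages; no confidence interval is mentioned. The Full Analysis set requires a post-baseline value of the primary endpoint, in the singular.

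**Purpose.** The background section says "The findings of this pilot study will help to design a randomised controlled clinical trial" of a bundle of exercise and supplement, to see whether it "can improve skeletal muscle mass, other markers of nutritional status and quality of life in people on haemodialysis".

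**The concern.** The intergroup sentence has nothing to act on. If it is a hidden subgroup plan, the groups could be picked after the data are seen. Candidates exist, for example "presence of diabetes and history of cardiovascular disease", but the plan collects these as baseline characteristics only.

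With no lead marker, no lead sample and no direction for the anti-inflammatory cytokines, nothing prevents a report from treating any one marker that moves favourably at p<0.05 as meeting the primary objective. Membership of the Full Analysis set is also unclear when CRP is available and the cytokines are not, or the reverse.

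A trial designer needs the size of the change, its uncertainty and its SD. A p-value from 15 people supplies none of these.

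**Working it through.** The sample size of 15 is described as pragmatic, with no power calculation, so there is no stated figure to reproduce. That omission is not criticised here.

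**Inputs from the documents:** n = 15; threshold 0.05 (taken as two-sided); CRP >5 mg/L at entry; no control; withdrawals not replaced.
**Assumptions:** panel size, correlation between marker changes, testing at both sampling times, and the CRP distribution. The documents give none of these.

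**1. Falsely favourable markers.** With no effect, each paired t-test has a 0.05/2 = 2.5% chance of a significant favourable change (t < -2.145 on 14 df). For k independent tests the chance of at least one is 1 - 0.975^k:
- k = 6: 1 - 0.975^6 = 14.1%
- k = 11: 1 - 0.975^11 = 24.3%
- k = 21: 1 - 0.975^21 = 41.2%

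For correlated changes, equicorrelated normal changes were simulated at n = 15:

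| Tests | Correlation 0 | 0.5 | 0.8 |
|---|---|---|---|
| 6 (CRP + 5 cytokines) | 14% | 11% | 7% |
| 11 (CRP + 10) | 24% | 16% | about 10% |
| 21 (CRP + 10, both sampling times) | 41% | 23% | 12% |

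The exact Wilcoxon test gives nearly the same rates. The correlation-0 column is an upper bound. It is least plausible for 21 tests, which include the same cytokines in the same people before and after dialysis.

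**2. Whether 2.5% applies to CRP.** It holds only for a marker not used to select participants. Suppose the qualifying CRP is also the baseline (the documents do not say). Assume ln CRP is normal with SD 1, an unselected median m of 5-8 mg/L, and test-retest correlation r of 0.6-0.9. With c = ln 5 - ln m, the expected change in ln CRP under no effect is -(1 - r) × φ(c)/(1 - Φ(c)).
- m = 5, r = 0.6: c = 0, ratio 0.798, change -0.4 × 0.798 = -0.319, a geometric mean ratio of exp(-0.319) = 0.73.
- m = 8, r = 0.9: c = -0.470, ratio 0.525, change -0.1 × 0.525 = -0.052, a geometric mean ratio of 0.95.

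Simulating the paired t-test at n = 15 under these inputs gives a significant fall in about 28% of trials in the first case and 6% in the second. Those are the extremes of the assumed range.

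**3. Precision, in SDs of the change.**
- 95% CI half-width for the mean change, all 15 complete: 2.145/√15 = 0.55 SD.
- If 12 complete: 2.201/√12 = 0.64 SD.
- 95% limits for the true SD at n = 15, assuming normal changes: √(14/χ² quantile on 14 df) = 0.73 to 1.58 times the observed SD.

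**4. An unstated subgroup test.** At two-sided 0.05 and 80% power, a 7 v 8 split detects a difference of 1.57 SD and a 5 v 10 split 1.66 SD.

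**The case against.** The strongest reply is that this is a small pilot meant to inform a later trial, and that no section says one significant marker is enough. This stands in part: the defect is a missing rule, not a stated lenient one. But the protocol sets a directional efficacy objective and a significance threshold and does not call the testing exploratory, so pilot status does not settle how the results will be claimed.

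The error rates depend on assumed panel sizes and correlations. That stands too; they are illustrations, and the upper ends are bounds.

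A reader might infer three stronger things that the documents do not support:
- **That the whole primary outcome is unnamed.** CRP is named first and is also the entry marker. Only the cytokines are unlisted.
- **That making CRP the single primary variable restores a 2.5% false-favourable rate.** Selection on CRP without a control group means it need not. Under the inputs above, the error from regression to the mean is similar in size to most of the multiplicity rates.
- **That the intergroup sentence reveals a second arm or a planned subgroup analysis.** Neither is described anywhere. The more likely explanation is generic wording, though that cannot be confirmed.

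**Conclusion.** The concern holds. The intergroup tests cannot be carried out as written in a one-group study with no defined subgroups. The primary outcome is CRP plus an unlisted, unranked cytokine set with no lead sample, and it is judged at 0.05 without a multiplicity rule, an exploratory label or an interval. These points rest on the text alone.

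The size is conditional. The chance of at least one falsely favourable marker is about 7%-14%, 10%-24% or 12%-41% for 6, 11 or 21 tests, over correlations from 0.8 down to 0. The 2.5% benchmark applies only to a marker not used for selection. For CRP, if the qualifying value serves as baseline, about 6%-28% of trials with no effect would show a significant fall under the assumed distribution. A single primary variable therefore removes the choice among markers, but it does not make an uncontrolled fall in CRP attributable to the supplement.

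This should be corrected, but it does not call the study's conduct into question.

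**What to change.** 1. Delete the intergroup sentence from the Synopsis and the Statistics section.
2. Name change in CRP from baseline to 6 weeks as the single primary variable, and define the Full Analysis set on it. Make the cytokines secondary or exploratory, listed by name, with one lead sampling time and a stated favourable direction for each. If several markers must stay primary, label the whole marker analysis exploratory and make no significance claim.
3. Report the paired change in ln CRP as a geometric mean ratio with 95% CI and the SD of the ln change, with Wilcoxon as sensitivity analysis; this also settles the open choice of test. Report changes in the other outcomes, including body composition and handgrip strength, with 95% CIs and SDs of change, since the later trial concerns muscle mass and nutritional status.
4. Where routine results already supply one, use a baseline CRP separate from the qualifying value. State that an uncontrolled fall in CRP cannot be attributed to the supplement, because it may reflect regression to the mean.

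Cost: wording in the Synopsis, Primary outcome and Statistics sections, with no added visits or samples. The downside is that cytokine results can no longer be called primary.
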